Statistical Analysis Plan

DRCR Retina Network Protocol AH: Single-Arm Study Assessing the Effects of Pneumatic Vitreolysis on Macular Hole

ClinicalTrials.gov Identifier: NCT03677869

Version Number	Author	Approver	Effective Date	Revision Description
1.0	[name]	[name]	09 Oct 2019	Initial SAP for Protocol version 2.0
2.0	[name]	[name]	19 Jan 2021	Revisions were made to accommodate a smaller than anticipated sample size after early stopping for safety concerns. Changes were made following review of study data. Details are provided in subsection 1.17. Applies to Protocol version 3.0.

SIGNATURES	
AUTHOR	
APPROVER	

1 **1.0 Overview**

2 The DRCR Retina Network Protocol AH study will evaluate the effectiveness of pneumatic
3 vitreolysis (PVL) in treating eyes with vitreomacular traction (VMT) and full-thickness macular
4 hole (MH). Presence of MH will be graded on optical coherence tomography (OCT) by a reading
5 center prior to enrollment and during follow-up. The primary outcome is at 8 weeks and follow-
6 up continues through 24 weeks.

7 **1.1 Statistical Hypotheses**

8 There are no formal statistical hypotheses that will be evaluated because this is a single-arm
9 study.

10 **1.2 Outcome Measures**

11 For the outcomes below, rescue treatment includes vitrectomy, ocriplasmin, or additional
12 pneumatic vitreolysis during the course of the study.

13 **1.2.1 Primary Efficacy Outcome:**

- 14 • Proportion of eyes with MH closure of the inner retinal layers* without rescue treatment
15 at 8 weeks.
 - 16 ○ For purposes of description only, the distribution of eyes by the following
17 categories at 8 weeks will be tabulated without statistical comparison:
 - 18 ▪ MH closure without rescue treatment
 - 19 ▪ MH closure with rescue treatment
 - 20 ▪ No MH closure and no rescue treatment
 - 21 ▪ No MH closure despite rescue treatment

22 **1.2.2 Secondary Efficacy Outcomes:**

- 23 • Proportion of eyes with MH closure of the inner retinal layers* without rescue treatment
24 through 24 weeks (time-to-event analysis).
- 25 • Proportion of eyes with central VMT release* without rescue treatment through 24 weeks
26 (time-to-event analysis).
 - 27 ○ For purposes of description only, the following will be tabulated without
28 statistical comparison at 8 weeks and 24 weeks:
 - 29 ▪ MH closure with central VMT release without rescue treatment
 - 30 ▪ MH closure without central VMT release without rescue treatment
 - 31 ▪ MH closure with central VMT release with rescue treatment
 - 32 ▪ MH closure without central VMT release with rescue treatment
- 33 • Mean change in visual acuity letter score from baseline at 8 and 24 weeks.

34 • Proportion of eyes with at least 10-letter gain (increase) in visual acuity from baseline at
35 8 and 24 weeks.

36 • Proportion of eyes with at least 10-letter loss (decrease) in visual acuity from baseline at
37 8 and 24 weeks.

38 • Proportion of eyes receiving rescue treatment before the 8-week visit.

39 • Proportion of eyes receiving rescue treatment before the 24-week visit.

40 ○ For purposes of description only, the following will be tabulated without
41 statistical comparison:

42 ■ Proportion of eyes receiving rescue treatment before the 24-week visit or
43 for which rescue treatment is planned at the 24-week visit and medical
44 records confirm rescue treatment occurred within the subsequent 12
45 weeks.

46 ■ Type of rescue treatment.

47 **1.2.3 Exploratory Outcomes:**

48 • Proportion of eyes with MH closure of the inner retinal layers with outer retinal lucency*
49 without rescue treatment at 8 and 24 weeks.

50 • Proportion of eyes with ellipsoid zone* integrity at 8 and 24 weeks.

51 ○ Both ellipsoid zone integrity within 1 mm of the center of the macula and at the
52 foveal center will be analyzed

53 *Determined by masked grader at the central reading center.

54 **1.3 Analysis Cohorts**

55 • Intention-To-Treat (ITT) Analysis Cohort: all enrolled participants irrespective of
56 treatment received.

57 • Safety Analysis Cohort: all enrolled participants irrespective of treatment received.

58 • Per-Protocol Analysis Cohort: only participants who complete the initial treatment (PVL)
59 and do not receive any non-protocol treatments during follow up. Vitrectomy performed
60 according to the criteria in section 4.2.1 of the protocol is considered per protocol and
61 eyes receiving this procedure will be included in the per-protocol cohort.

62 The primary analysis will follow the ITT principle and include all enrolled participants.

63 A per-protocol analysis will be performed to provide additional information regarding the
64 magnitude of the treatment effect. The per-protocol analysis will only be performed if at least
65 10% of enrolled participants would be excluded by these criteria (e.g., 5 or more participants if
66 exactly 50 are enrolled).

67 The ITT analysis is considered the primary analysis. If the results of the per-protocol and ITT
68 analyses give inconsistent results, then the per-protocol analysis will be interpreted with caution.
69 In this scenario, exploratory analyses will be performed to evaluate possible factors contributing
70 to the difference.

71 **1.4 Analysis of the Primary Efficacy Outcome**

72 The primary outcome of MH closure of the inner retinal layers without rescue treatment through
73 8 weeks is a binary variable that is graded by the central reading center. The proportion of eyes
74 meeting the primary outcome will be determined and the 95% Wilson (score) confidence interval
75 will be calculated.¹⁻³

76 Since the chance of re-opening after closure before 8 or 24 weeks is highly unlikely, an eye with
77 MH closure of the inner retinal layers without rescue treatment at any time prior to 24 weeks will
78 be considered to have met the outcome through 24 weeks if the participant is lost to follow-up.
79 Similarly, any eye receiving rescue treatment prior to 24 weeks will be considered not to have
80 met the outcome through 24 weeks.

81 Multiple imputation will be used to impute missing data for eyes lost to follow-up that did not
82 have prior MH closure or rescue treatment documented. The imputation model will include MH
83 status at 1, 4, 8, and 24 weeks.

84 A sensitivity analysis will be conducted using the same approach as above, but without multiple
85 imputation (i.e., complete-case analysis).

86 **1.5 Analysis of the Secondary and Exploratory Outcomes**

87 The ITT analysis cohort will be used for all secondary and exploratory outcomes.

88 **1.5.1 Secondary Efficacy Outcomes**

89 There are two time-to-event outcomes to be evaluated through 24 weeks: (1) macular hole
90 closure of the inner retinal layers without rescue treatment and (2) central VMT release without
91 rescue treatment. Each of these outcomes will be graded by the central reading center. For each
92 outcome, a Kaplan-Meier curve will be constructed and the cumulative probability of the
93 outcome with 95% confidence interval will be estimated for the final time point. Data from eyes
94 not observed to meet the outcome or that receive rescue treatment will be censored on the date of
95 their final visit (not the date of rescue treatment). The analysis of central VMT release without
96 rescue treatment will be limited to eyes with central VMT at baseline. Because the chance of re-
97 attachment after release before 8 or 24 weeks is highly unlikely, an eye with release without
98 rescue treatment at any time prior to 24 weeks will be considered to have met the outcome
99 through 24 weeks if the participant is lost to follow-up. Similarly, any eye receiving rescue
100 treatment prior to 24 weeks will be considered not to have met the outcome through 24 weeks.

101 Change in visual acuity letter score from baseline at 8 and 24 weeks is a continuous outcome.
102 The mean and 95% confidence interval will be calculated for each time point. Missing data will
103 be imputed with multiple imputation. The imputation model will baseline visual acuity, visual
104 acuity at 1, 4, 8, and 24 weeks, and MH status at 1, 4, 8, and 24 weeks.

105 The proportions of eyes with at least 10-letter gain (increase) and least 10-letter loss (decrease)
106 in visual acuity from baseline at 8 and 24 weeks are binary variables. Wilson (score) 95%
107 confidence intervals will be calculated for each outcome at both time points. The imputed data
108 sets described above for the mean change in visual acuity from baseline will be utilized.³

109 The proportion of eyes receiving rescue treatment before 8 and 24 weeks is a binary variable.
110 Wilson (score) 95% confidence intervals will be calculated for each time point. Complete-case
111 analysis (no imputation of missing data) will be used for this outcome.

112 **1.5.2 Exploratory Efficacy Outcomes**

113 The proportion of eyes with MH closure of the inner retinal layers with outer retinal lucency at 8
114 and 24 weeks is a binary variable graded by the central reading center. Wilson (score) 95%
115 confidence intervals will be calculated for each time point. Complete-case analysis (no
116 imputation of missing data) will be used for this outcome.

117 The proportion of eyes with ellipsoid zone integrity at 8 and 24 weeks is a binary variable graded
118 by the central reading center (loss of integrity and no loss of integrity). Both ellipsoid zone
119 integrity within 1 mm of the center of the macula and in the foveal center will be analyzed.
120 Wilson (score) 95% confidence intervals will be calculated for each time point. Complete-case
121 analysis (no imputation of missing data) will be used for this outcome.

122 **1.6 Safety Analyses**

123 All reportable adverse events will be categorized as study eye or systemic. All events will be
124 tabulated in a listing of each reported Medical Dictionary for Regulatory Activities (MedDRA)
125 term and summarized over each MedDRA System Organ Class. All enrolled participants will be
126 included in safety analyses. Any events occurring between enrollment and study treatment will
127 be counted. The number of adverse events (ocular or systemic) considered related to treatment
128 will be tabulated.

129 **1.6.1 Ocular Adverse Events**

130 The frequency of each ocular adverse event occurring at least once per eye will be calculated.
131 The proportion of eyes experiencing each outcome will be calculated along with 95% Wilson
132 (score) confidence intervals. The following ocular adverse events are of primary interest:

- 133
 - Endophthalmitis
 - 134 ○ Retinal detachment
 - 135 ○ Retinal tear
 - 136 ○ Traumatic cataract
 - 137 ○ Cataract extraction in eyes phakic at baseline
 - 138 ○ Vitreous hemorrhage
 - 139 ○ Adverse intraocular pressure (IOP) events (composite outcome)
 - 140 ■ Increase in IOP \geq 10 mmHg from baseline (at a follow-up visit)
 - 141 ■ IOP \geq 30 mmHg (at a follow-up visit)
 - 142 ■ Initiation of medication to lower IOP that was not in use at baseline
 - 143 ■ Glaucoma procedure

144 **1.6.2 Systemic Adverse Events**

145 The frequency of each systemic adverse event occurring at least once per participant will be
146 calculated. The following systemic adverse events are of primary interest:

147

- Death

- Serious adverse event (at least one)

The following systemic adverse events are of secondary interest:

- For each MedDRA System Organ Class, proportion of participants with at least one serious adverse event

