319 eye is only required at the 8 week visit. When a refraction is not performed, the most
320 recently performed refraction is used for the testing.
321 2. Spectral-Domain OCT using Zeiss Cirrus or Heidelberg Spectralis on the study eye
322 • The same machine type (Cirrus or Spectralis) used at baseline must be used during follow
323 up.
324 3. Ocular exam in the study eye only, including slit lamp examination with lens assessment,
325 measurement of IOP, and dilated ophthalmoscopy
326 • The eye exam should be extensive enough to identify adverse events of interest
327 • An extended ophthalmoscopy including a scleral depression is required at 1, 4, and 8
328 weeks to identify any retinal tears or detachments
329 All of the testing procedures do not need to be performed on the same day, provided that they are
330 completed within the time window of a visit. If data from a testing procedure is unusable (e.g., if
331 OCT is ungradable), the participant may be asked to repeat the procedure during an additional
332 visit, whether part of usual care or solely to repeat the procedure.

333 **4.1.2 Unscheduled Visits**

334 Additional visits may occur as required for usual care of the study participant.

335 Testing procedures at unscheduled visits are at investigator discretion. However, it is
336 recommended that procedures performed should follow the standard DRCR Retina Network
337 protocol.

338 **4.2 Treatment During Follow Up**

339 **4.2.1 Criteria for Vitrectomy**

340 Vitrectomy should not be performed due to failure of macular hole closure prior to 4 weeks
341 without chair approval. Between 4 and 8 weeks, vitrectomy may only be performed (but is not
342 required) if the macular hole size is not improving from baseline. After 8 weeks, vitrectomy can
343 be performed at investigator discretion.

344 **4.2.2 Treatment for Other Conditions in the Study Eye**

345 An eye should not be enrolled that is anticipated to require intraocular treatment for another
346 condition during the study. If a condition requiring prompt treatment develops during follow up,
347 the treatment is at investigator discretion.

348 **4.2.3 Treatment in the Non-Study Eye**

349 Treatment in the non-study eye is at investigator discretion, except that gas injection for VMT is
350 not permitted in the non-study eye during the study.

351

CHAPTER 5: STUDY DEVICE

352 **5.1 Description of the Investigational Device**

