512 The study may be discontinued by the Executive Committee (with approval of the DSMC) prior
513 to the preplanned completion of follow up for all study participants.

514 **6.6 Independent Safety Oversight**

515 A Data and Safety Monitoring Committee will approve the protocol, template Informed Consent
516 Form, and substantive amendments and provide independent monitoring of adverse events.
517 Cumulative adverse event data are tabulated semi-annually for review by the DSMC. Following
518 each DSMC data review, a summary will be provided to IRBs. A list of specific adverse events
519 to be reported expeditiously to the DSMC will be compiled and included as part of the DSMC
520 Monitoring Plan document.

521 **6.7 Risks**

522 The potential risks associated with use of the study device are described in section 1.4.1.

523 Additional risks are minor or infrequent and include the following:

524 **Risks Related to Testing Procedures**

525 Many of the testing procedures in this study are part of daily ophthalmologic practice in the
526 United States and pose few if any known risks.

527 • Dilating eye drops will be used as part of the exam. There is a small risk of inducing a
528 narrow-angle glaucoma attack from the pupil dilation. However, all participants will have
529 had prior pupil dilation usually on multiple occasions and therefore the risk is extremely
530 small.

531 **Risks Related Specifically to the Pre-Injection Preparation**

532 • There are potential side effects to subconjunctival anesthetic, which are rare. They include,
533 but are not limited to, the following: damage to the eyeball by the needle, damage to the optic
534 nerve, double vision lasting 24 hours or more.

535 • Complications associated with paracentesis are uncommon, but may include uveitis, flat
536 anterior chamber, corneal wound leak, hyphema, anterior vitreous prolapse, or pupillary
537 block glaucoma and cataract. Under certain circumstances, such complications may lead to
538 vision loss.

539 **Risks if Pregnant**

540 According to the C₃F₈ package insert, there are no known teratogenic effects when injected into
541 the eye; however, caution should be used in pregnant women. Therefore, patients will not be
542 allowed to participate in this study if pregnant. Women who become pregnant during the study
543 will be asked to stay in the study since there is no follow-up treatment with the investigational
544 product.

545 **CHAPTER 7: MISCELLANEOUS CONSIDERATIONS**

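### The per-protocol exclusion runs to 24 weeks although the analysis concerns only the 8-week outcome, so treatment given after an eye's result is known can remove that eye

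*SAP*

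**What the plan says.** **Cohort rule.** SAP 1.3 admits to the per-protocol cohort participants who complete the initial PVL "and do not receive any non-protocol treatments during follow up. Vitrectomy performed" "according to the criteria in section 4.2.1 of the protocol is considered per protocol and" such eyes are kept. Protocol 8.5 states the same rule. No other treatment is exempted by name, and no end date is given beyond follow-up itself.

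**Time scale.** SAP 1.0 separates the two time points: "center prior to enrollment and during follow-up. The primary outcome is at 8 weeks and follow"-up then goes on to 24 weeks.

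**Use of the cohort.** SAP 1.5 states: "The ITT analysis cohort will be used for all secondary and exploratory outcomes". Safety has its own cohort. That leaves the 8-week primary outcome as the only place for the per-protocol analysis.

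**Rescue.** SAP 1.2 reads "For the outcomes below, rescue treatment includes vitrectomy, ocriplasmin, or additional" PVL. SAP 1.4 defines the primary outcome as closure without rescue through 8 weeks. For the later time point it adds "Similarly, any eye receiving rescue treatment prior to 24 weeks will be considered not to have" met the outcome through 24 weeks.

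**Vitrectomy criteria.** Protocol 4.2.1 begins "Vitrectomy should not be performed due to failure of macular hole closure prior to 4 weeks" unless the chair approves. Between 4 and 8 weeks it is allowed only if the hole is not improving. After 8 weeks it is left to the investigator.

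**When the analysis runs.** SAP 1.3 requires that at least 10% of enrolled participants would be excluded (5 of 50). Its stated purpose is to inform the size of the treatment effect. ITT is primary, and if the two analyses are inconsistent the per-protocol result is read with caution and the reasons explored.

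**The concern.** A per-protocol analysis removes participants whose result may have been distorted by departures from the planned treatment. A treatment given after the outcome has been assessed cannot have distorted it. Removing an eye for such a treatment selects on what happened later, and what happens later depends on the result: an eye still open at 8 weeks is the one most likely to be treated again.

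The rule also separates eyes with identical 8-week results by the later choice of procedure. Vitrectomy after 8 weeks always meets Protocol 4.2.1, so that eye stays in. Repeat PVL or ocriplasmin is not covered by the exemption, so on the most natural reading that eye leaves.

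At stake is a supportive figure. The per-protocol closure rate would be reported as information on the size of the effect, while part of any gap from ITT could come from removing known failures. The 10% trigger is affected too, because late treatments count towards it and could by themselves cause the analysis to be run.

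**Working it through.** **1. The plan's own precision.** Protocol Table 1 gives half-widths for 50 eyes of 12.3 points at 70% closure and 13.4 at 50%. The Wilson half-width is z/(1 + z²/n) × √[p(1−p)/n + z²/(4n²)], with z = 1.96 and n = 50.

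- p = 0.70: (1.96/1.0768) × √(0.0042 + 0.000384) = 12.3 points.
- p = 0.50: (1.96/1.0768) × √(0.0050 + 0.000384) = 13.4 points.

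Both match, so the table uses the interval planned in SAP 1.4.

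**2. The same eye under two later treatments.** Take an eye assessed on schedule at day 56, hole open, no rescue so far. It is a failure for the primary outcome. At week 10 (day 70) it is treated.

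| Treatment at week 10 | 8-week result | Per-protocol cohort |
|---|---|---|
| None | failure | kept |
| Vitrectomy (at discretion, Protocol 4.2.1) | failure | kept |
| Repeat PVL or ocriplasmin (no exemption) | failure | dropped |

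The 8-week result is the same in every row; only the later choice differs.

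**3. Effect on the estimate.** Let N be enrolled, s successes, m excluded, and k of those m failures. ITT is p = s/N and per-protocol is (s − (m − k))/(N − m). The second exceeds the first exactly when k/m > 1 − p. At 60% closure the shift is upward only if more than 40% of excluded eyes are failures.

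The documents give no count of such treatments, so m and k are assumptions. With N = 50, s = 30 (60.0%, Wilson 46.2 to 72.4) and m = 5, which just meets the trigger:

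| Failures among the 5 excluded (others successes) | Per-protocol | Shift (points) |
|---|---|---|
| 5 | 30/45 = 66.7% (52.1 to 78.6) | +6.7 |
| 3 | 28/45 = 62.2% (47.6 to 74.9) | +2.2 |
| 2 | 27/45 = 60.0% (45.5 to 73.0) | 0 |
| 1 | 26/45 = 57.8% (43.3 to 71.0) | −2.2 |

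With all 5 failures, the shift at other closure rates is:

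- 50%: 25/50 to 25/45 = 55.6%, +5.6 points.
- 70%: 35/50 to 35/45 = 77.8%, +7.8 points.

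**4. A smaller study.** The SAP 2.0 revision note reports a smaller sample than anticipated but no figure. At an assumed 30 eyes, 3 exclusions meet the trigger. If all 3 are failures, 18/30 = 60.0% (42.3 to 75.4) becomes 18/27 = 66.7% (47.8 to 81.4).

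**5. With a cut-off.** If the 5 eyes in step 3 were all treated after their 8-week visit, none would be excluded. The trigger would not be met, the per-protocol analysis would not run, and 60.0% would stand.

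**The case against.** **Few eyes may be affected.** Protocol 1.1.2 calls vitrectomy the first-line therapy and reports major concerns about ocriplasmin, so late treatment may mostly be vitrectomy, which stays in. This stands: the size is unknown and may be nil.

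**Safeguards exist.** ITT is primary, no hypothesis is tested, and type of rescue and protocol deviations are tabulated. This stands as a limit on importance. But the caution clause applies only when results are inconsistent, which is not defined. At 50 to 70% closure, shifts of 5.6 to 7.8 points lie inside the Table 1 half-widths and might not be called inconsistent.

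**The term is not itemised.** Neither document lists the non-protocol treatments. A reader might take Protocol 6.7, "since there is no follow-up treatment with the investigational" product, as a rule against repeat PVL. It is not one: the sentence explains why women who become pregnant stay in the study. The reading used here rests on the single exemption in SAP 1.3 and on Protocol 4.2.1 giving criteria for vitrectomy alone. The missing cut-off does not depend on it, since any treatment counted as non-protocol raises the same problem after 8 weeks.

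**Early exclusions are proper.** A reader might infer that dropping eyes rescued before 8 weeks is also an error, because rescue is part of the failure definition. The documents do not support that. Vitrectomy before 4 weeks without approval, or on an improving hole, ends the chance of unaided closure, so the counted failure may reflect the breach and not PVL. Excluding such eyes is a defensible per-protocol choice.

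**A change now follows data review.** True, but SAP 2.0 already made changes after data review and disclosed them in SAP 1.17.

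**Conclusion.** The point holds for the time limit. As written, the per-protocol cohort for an 8-week outcome depends on treatments given up to 24 weeks, and nothing else in either document adds a cut-off. It is a cheap improvement to a conditional, supportive analysis; the primary result is untouched.

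The illustrated shift of +6.7 points (60.0% to 66.7%) assumes 50 eyes, exactly 5 excluded, and all 5 being 8-week failures. It shrinks or reverses if some excluded eyes are successes, and there is no effect if the 10% trigger is not met.

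Two stronger readings should be resisted. First, the bias need not be upward: both documents tabulate closure without central release of vitreomacular traction, so a closed eye could later be treated for persisting traction and be dropped as a success. Second, vitrectomy outside Protocol 4.2.1 does not add to the problem after 8 weeks, because from then on it is at the investigator's discretion.

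**What to change.** In SAP 1.3, replace the open-ended follow-up period in the exclusion with: *before the eye's 8-week analysis visit (SAP 1.13), or before the end of the 8-week analysis window if that visit is missed*. The cut-off should be each eye's own visit, not a calendar week, because the SAP 1.13 window runs from day 42 to day 126. Apply the same cut-off when counting towards the 10% trigger. Record the change in SAP 1.17 as made after data review and as superseding Protocol 8.5 on this point.

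Exclusion for non-protocol rescue before the 8-week outcome may stay. In either case, report for each excluded eye the reason, the timing relative to the 8-week visit, and its ITT outcome.

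The cost is a few sentences and no new data, since rescue timing is already needed for the outcomes before 8 and 24 weeks. The downside is fewer exclusions, so the trigger is less likely to be met and the per-protocol analysis may not run.
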